8.2.4. Adverse Event Summaries

An overall summary of TEAEs by treatment group will include the following:

- Number (%) of participants who had any TEAEs
- Number (%) of participants who had any serious TEAEs
- Number (%) of participants who had any Grade 3 or 4 TEAEs
- Number (%) of participants who had any fatal TEAEs
- Number (%) of participants who had any TEAEs related to tafasitamab/placebo
- Number (%) of participants who had any serious TEAEs related to tafasitamab/placebo
- Number (%) of participants who had any Grade 3 or 4 TEAEs related to tafasitamab/placebo
- Number (%) of participants who had any fatal TEAEs related to tafasitamab/placebo
- Number (%) of participants who had any TEAEs related to lenalidomide
- Number (%) of participants who had any serious TEAEs related to lenalidomide
- Number (%) of participants who had any Grade 3 or 4 TEAEs related to lenalidomide
- Number (%) of participants who had any fatal TEAEs related to lenalidomide
- Number (%) of participants who had any TEAEs related to rituximab

- Number (%) of participants who had any serious TEAEs related to rituximab
- Number (%) of participants who had any Grade 3 or 4 TEAEs related to rituximab
- Number (%) of participants who had any fatal TEAEs related to rituximab
- Number (%) of participants who had any TEAE leading to interruption of tafasitamab/placebo
- Number (%) of participants who had any TEAE leading to interruption of lenalidomide
- Number (%) of participants who had any TEAE leading to interruption of rituximab
- Number (%) of participants who had any TEAE leading to dose delay of tafasitamab/placebo
- Number (%) of participants who had any TEAE leading to dose delay of rituximab
- Number (%) of participants who had any TEAE leading to permanent discontinuation of tafasitamab/placebo
- Number (%) of participants who had any TEAE leading to permanent discontinuation of lenalidomide
- Number (%) of participants who had any TEAE leading to permanent discontinuation of rituximab
- Number (%) of participants who had any TEAE leading to dose reduction of lenalidomide

The following summaries will be produced by MedDRA term (if 10 or fewer participants appear in a table, a listing may be produced instead):

- Summary of TEAEs by MedDRA SOC and PT
- Summary of TEAEs by MedDRA PT in decreasing order of frequency
- Summary of TEAEs by MedDRA SOC, PT, and maximum severity
- Summary of Grade 3 or 4 TEAEs by MedDRA SOC and PT
- Summary of Grade 3 or 4 TEAEs by MedDRA PT in decreasing order of frequency
- Summary of TEAEs with a fatal outcome by MedDRA SOC and PT
- Summary of serious TEAEs by MedDRA SOC and PT
- Summary of serious TEAEs by MedDRA PT in decreasing order of frequency
- Summary of tafasitamab/placebo treatment-related TEAEs by MedDRA SOC and PT
- Summary of lenalidomide treatment-related TEAEs by MedDRA SOC and PT
- Summary of rituximab treatment-related TEAEs by MedDRA SOC and PT
- Summary of tafasitamab/placebo treatment-related TEAEs by MedDRA PT in decreasing order of frequency

- Summary of lenalidomide treatment-related TEAEs by MedDRA PT in decreasing order of frequency
- Summary of rituximab treatment-related TEAEs by MedDRA PT in decreasing order of frequency
- Summary of Grade 3 or 4 tafasitamab/placebo treatment-related TEAEs by MedDRA SOC and PT
- Summary of fatal tafasitamab/placebo treatment-related TEAEs by MedDRA SOC and PT
- Summary of Grade 3 or 4 lenalidomide treatment-related TEAEs by MedDRA SOC and PT
- Summary of fatal lenalidomide treatment-related TEAEs by MedDRA SOC and PT
- Summary of Grade 3 or 4 rituximab treatment-related TEAEs by MedDRA SOC and PT
- Summary of fatal rituximab treatment-related TEAEs by MedDRA SOC and PT
- Summary of tafasitamab/placebo treatment-related serious TEAEs by MedDRA SOC and PT
- Summary of lenalidomide treatment-related serious TEAEs by MedDRA SOC and PT
- Summary of rituximab treatment-related serious TEAEs by MedDRA SOC and PT
- Summary of TEAEs leading to lenalidomide dose reduction by MedDRA SOC and PT
- Summary of TEAEs leading to tafasitamab/placebo dose interruption by MedDRA SOC and PT
- Summary of TEAEs leading to lenalidomide dose interruption by MedDRA SOC and PT
- Summary of TEAEs leading to rituximab dose interruption by MedDRA SOC and PT
- Summary of TEAEs leading to tafasitamab/placebo dose delay by MedDRA SOC and PT
- Summary of TEAEs leading to rituximab dose delay by MedDRA SOC and PT
- Summary of TEAEs leading to discontinuation of tafasitamab/placebo by MedDRA SOC and PT
- Summary of TEAEs leading to discontinuation of lenalidomide by MedDRA SOC and PT
- Summary of TEAEs leading to discontinuation of rituximab by MedDRA SOC and PT

- Summary of AESIs for tafasitamab/placebo and lenalidomide (eCRF) by grouped term and PT
- Summary of AESIs for tafasitamab/placebo and lenalidomide by grouped term and PT

The following groups will be displayed for the FL, MZL, and overall populations:

- Age group ($< 65 \text{ vs} \ge 65 \text{ years}$, $< 75 \text{ vs} \ge 75 \text{ years}$), sex, race and MZL subtype (for MZL population only) will be displayed for the following tables:
 - Overall Summary of TEAEs
 - Summary of TEAEs by MedDRA SOC and PT
 - Summary of Serious TEAEs by MedDRA SOC and PT
 - Summary of Grade 3 or 4 TEAEs by MedDRA SOC and PT
 - Summary of TEAEs with a fatal outcome by MedDRA SOC and PT
- Creatinine Clearance (≥ 30 and < 60 ml/min vs ≥ 60) will be displayed for the following tables:
 - Overall Summary of TEAEs
 - Summary of TEAEs by MedDRA SOC and PT
 - Summary of Serious TEAEs by MedDRA SOC and PT
 - Summary of Grade 3 or 4 TEAEs by MedDRA SOC and PT
 - Summary of TEAEs with a fatal outcome by MedDRA SOC and PT
 - Summary of lenalidomide treatment related TEAEs by MedDRA SOC and PT
 - Summary of TEAEs leading to lenalidomide dose reduction by MedDRA SOC and PT
 - Summary of TEAEs leading to discontinuation of lenalidomide by MedDRA SOC and PT

In addition, the following summaries will be produced:

Selected hematological TEAEs (neutropenia, febrile neutropenia, anemia, thrombocytopenia) of Grade 3 or 4 and fatal by SOC, PT, and grade.

- PTs used to identify neutropenia: "neutropenia," "neutrophil count decreased"
- PTs used to identify anemia: "anemia," "red blood cell count decreased"
- PTs used to identify thrombocytopenia: "platelet count decreased,"
 "thrombocytopenia"
- PTs used to identify febrile neutropenia: "febrile neutropenia"

- Duration of TEAEs of the selected PTs and customized MedDRA queries:
 - Neutropenia ≥ Grade 3 (PTs "neutropenia," "neutrophil count decreased")
 - Thrombocytopenia ≥ Grade 3 (PTs "thrombocytopenia," "platelet count decreased")
 - Infections and infestations ≥ Grade 3 (SOC "infections and infestations")
 - Infective pneumonia ≥ Grade 3 (SMQ code 20000231, narrow scope)
 - Urinary tract infection ≥ Grade 3 (HLT "bladder infections and inflammations,"
 HLT "Genitourinary infections and inflammations NEC," HLT
 "Glomerulonephritis and nephrotic syndrome")
 - Sepsis ≥ Grade 3 (SMQ "sepsis" and SMQ "agranulocytosis")
 - Febrile neutropenia, all grades (PT "febrile neutropenia")
 - Thromboembolic event, all grades (SMQ code 2000081)
 - Thromboembolic event ≥ Grade 3 (SMQ code 2000081)
 - Opportunistic infections ≥ Grade 3 (SMQ "opportunistic infections")

Selected AEs included in the previous summaries will be listed as a reference.

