10.4.2. Safety Analyses

Safety analyses will be conducted for the SAF. No formal statistical testing will be performed.

[figure not shown]
All TEAEs, clinical laboratory measurements, vital sign measurements, and abnormal ECGs will be summarized by treatment group. Quantitative safety variables and their changes from baseline (laboratory and vital signs) will be summarized with descriptive statistics. Abnormal values outside of established ranges will be flagged and tabulated based on predefined criteria.

Measures of exposure (eg, days of exposure, dose intensity) of tafasitamab/placebo, lenalidomide, and rituximab will be summarized descriptively.

Adverse events will be coded by the MedDRA dictionary and severity of AEs will be based on the NCI CTCAE v5.0 using Grades 1 through 5. A TEAE is defined as an AE either reported for the first time or worsening of a pre-existing event on or after first dose of study treatment and within 90 days of the last administration of study treatment. Number (%) of participants reporting any TEAEs, any serious TEAEs, any Grade 3 or higher TEAEs, any treatment-related TEAEs, any treatment-related serious TEAEs, any treatment-related Grade 3 or higher TEAEs, any fatal TEAEs, and any TEAEs leading to treatment interruption/delay/dose reduction/discontinuation will be tabulated by MedDRA system organ class and preferred term. Data listings will include all AEs regardless of their timing to study drug/treatment administration.

The clinical laboratory data will be analyzed using summary statistics; no formal treatment group comparisons are planned. In addition, distributions of key laboratory parameters may be plotted over time; these values will also be classified into CTCAE toxicity grades when applicable, and tabulated.

Descriptive statistics and mean change from baseline will be determined for vital signs at each assessment time. The abnormal values for participants exhibiting vital sign abnormalities will be listed.

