2.2.5.x	Summary of Minimal Residual Disease- Negativity Rate in Peripheral Blood at End of Treatment	MRD-blood evaluable	X	X	X	X	X	
2.2.6.x	Sensitivity Analysis for Summary of Minimal Residual Disease Negativity Rate in Peripheral Blood	MRD-blood evaluable	X		X	X	X	
2.2.7.x	Sensitivity Analysis for Summary of Minimal Residual Disease Negativity Rate in Bone Marrow	MRD-bone marrow evaluable	X		X	X	X	
2.2.8.x	Summary of Overall Response Rate by Investigator Assessment	FAS	X	X	X	X	X	
2.2.9.x	Summary of Overall Response Rate by IRC	FAS	X	X	X	X	X	
2.2.10.x	Sensitivity Analysis for Summary of Overall Response Rate by Investigator Assessment	FAS	X		X	X	X	
2.2.11.x	Summary of Duration of Response by Investigator Assessment	FAS	X	X	X	X	X	
2.2.12.x	Summary of Duration of Response by IRC	FAS	X	X	X	X	X	
2.2.13.x	Sensitivity Analysis for Summary of Duration of Response by Investigator Assessment	FAS	X		X	X	X	
2.2.14.x	Summary of Concordance Rates Between Investigator Assessment and IRC Review	FAS	X	X	X	X	X	
2.2.15.x	Summary of Currentness of Progression- Free Survival and Overall Survival	FAS	X		X	X	X	
2.2.16.x	Summary of Progression-Free Survival and Overall Survival Follow-Up Time	FAS	X		X	X	X	
2.2.17.x	Summary of Quality of Life Assessments - EORTC QLQ-C30	FAS	X		X	X	X	
2.2.18.x	Summary of Quality of Life Assessments - EQ-5D-5L	FAS	X		X	X	X	
2.2.19.x	Summary of Quality of Life Assessments - FACT-Lym	FAS	X		X	X	X	
2.3.3.x	Summary of Post-Treatment Systemic Antilymphoma Therapies	FAS	X		X	X	X	

Table No.	Title	Pop	FL	MZL	Overall	Jap FL	Jap Overall	Standard
		ı		1	1	ı	ı	ı
2.90.4.x	Summary of Progression-Free Survival by Investigator Assessment in PPS	PPS	X	X	X	X	X	
2.90.8.x	Summary of Overall Survival in PPS	PPS	X	X	X	X	X	
Safety								
3.1.1.x	Summary of Exposure to Tafasitamab/Placebo	SAF	X	X	X		X	X
3.1.2.x	Summary of Exposure to Rituximab	SAF	X	X	X		X	X
3.1.3.x	Summary of Exposure to Lenalidomide	SAF	X	X	X		X	X
3.1.4.x	Summary of Exposure to Lenalidomide by Creatinine Clearance	SAF	X	X	X		X	X
3.2.1.x	Overall Summary of Treatment- Emergent Adverse Events	SAF	X	X	X		X	X
3.2.2.x	Summary of Treatment-Emergent Adverse Events by MedDRA SOC and	SAF	X	X	X		X	X
3.2.3.x	Preferred Term Summary of Treatment-Emergent	SAF	X	X	X		X	X
	Adverse Events by MedDRA Preferred							
3.2.4.x	Term in Decreasing Order of Frequency Summary of Treatment-Emergent	SAF	X	X	X		X	X
	Adverse Events by MedDRA SOC, Preferred Term, and Maximum Severity							

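### The SAP's severe-TEAE rows and tables stop at Grade 4, so the Grade 3 or higher incidence set out in the protocol has no row of its own, and for treatment-related events it can only be bounded from the planned tables

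*SAP*

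**What the plan says.** Protocol 10.4.2 lists the participant counts to be tabulated by SOC and PT. They include "any Grade 3 or higher TEAEs, any treatment-related TEAEs, any treatment-related serious TEAEs, any treatment-related Grade 3 or higher TEAEs, any fatal TEAEs". The same section says that "severity of AEs will be based on the NCI CTCAE v5.0 using Grades 1 through 5", and Protocol 9.3 defines Grade 5 as fatal. The protocol's severe category therefore includes fatal events, and fatal TEAEs are a further, separate item.

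SAP 8.2.4 splits that category. Its overall summary has one row for "Number (%) of participants who had any Grade 3 or 4 TEAEs" and another for "Number (%) of participants who had any fatal TEAEs", and repeats the pair for events related to tafasitamab/placebo, lenalidomide and rituximab. The SOC/PT displays follow suit, for example "Summary of Grade 3 or 4 tafasitamab/placebo treatment-related TEAEs by MedDRA SOC and PT", with a separate fatal table for each drug. In Appendix A the Grade 3 or 4 tables are 3.2.5 and 3.2.6 (all-cause) and 3.2.15, 3.2.17 and 3.2.19 (related to each drug).

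SAP 10.1, which records changes to protocol-defined analyses, says nothing about the threshold.

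**The concern.** Comparing the incidence and severity of TEAEs between arms is a secondary objective in both documents. If severe toxicity is read from the Grade 3 or 4 row, a participant whose only severe event was fatal is missing from it. If a reader adds the fatal row to compensate, anyone with both kinds of event is counted twice. Neither reading gives the figure that the protocol specified.

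The narrower threshold is not a study-wide convention. Protocol 5.6 directs the IDMC's safety review to events of Grade 3 and above, and SAP 8.2.4 itself uses Grade 3 and above for most of its duration summaries.

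**Working it through.** The documents give no numerical figure on this point to reproduce. The check compares the planned displays and then applies set arithmetic.

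**1. Can the overall summary give the protocol's figure?** For any arm,

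n(Grade ≥3) = n(Grade 3 or 4) + n(fatal) − n(both).

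The summary gives the first two terms but not n(both). So n(Grade ≥3) is at least the larger of n(Grade 3 or 4) and n(fatal), and at most their sum. The Grade 3 or 4 row falls short by the number of participants whose only Grade ≥3 event was fatal, which lies between 0 and n(fatal).

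**2. Does another table supply it?**

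| Protocol item | Planned source | Result |
|---|---|---|
| All-cause Grade ≥3 by SOC and PT | "Summary of TEAEs by MedDRA SOC, PT, and maximum severity" (Table 3.2.4) | Derivable: add the Grade 3, 4 and 5 counts |
| All-cause Grade ≥3, any term | Overall summary (Table 3.2.1) | Bounded only; Table 3.2.4 would settle it if it has an any-TEAE total row |
| Treatment-related Grade ≥3 | Grade 3 or 4 and fatal displays for each drug | Bounded only; no treatment-related maximum-severity table is planned |

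The first result assumes the usual convention that each participant counts once per term, at the worst grade. The table shells are in a separate document, so neither this nor the total row can be confirmed.

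**3. Scale, for illustration only.** Protocol 2.1.4.6 reports 3 participants (3.7%) who died on treatment of AEs in the single-arm DLBCL study of tafasitamab plus lenalidomide. The denominator of about 81 is inferred from the percentages (3/81 = 3.7%). The Clopper-Pearson 95% interval is 0.8% to 10.4%. With about 618 randomized participants, each arm has 618/2 = 309:

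- point estimate: 3.7% × 309 = 11.4, about 11 participants with a fatal AE
- interval: 0.8% to 10.4% of 309, about 2 to 32 participants.

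These are participants with a fatal AE, not participants missing from the Grade 3 or 4 row. To be missing, a participant must also have had no Grade 3 or 4 TEAE. If, as an assumption, 60% of an arm had a Grade 3 or 4 TEAE and 3.7% a fatal one, Grade ≥3 incidence would lie between 60.0% (every fatal case also had a Grade 3 or 4 event) and 63.7% (none did). If the two were independent it would be 60% + 40% × 3.7% = 61.5%. With 50% or 70% in place of 60%, the independent case gives 51.9% or 71.1%.

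**The case against.** The strongest reply is that nothing is lost. Fatal TEAEs have their own row in the same overall summary, all-cause and for each drug, and their own tables, such as "Summary of TEAEs with a fatal outcome by MedDRA SOC and PT". Showing them apart makes an imbalance in deaths easier to see. This stands. A reader might infer that every SAP table stops at Grade 4, or that fatal cases drop out of the safety report, and the documents support neither. Table 3.2.4 spans all grades, the AESI tables are by maximum severity, the selected hematological summary covers fatal events, and several duration summaries and the hypersensitivity AESI use Grade 3 and above.

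It is also fair to say that the omission may be small. Protocol 9.3 asks for a new AE record when severity changes over a reporting period, so an event that worsens to death may leave its own Grade 3 or 4 record. Grade 3 or higher neutropenia was common in First-MIND (54.5% and 66.7% in its two arms), although with CHOP. Many fatal cases may therefore already be in the Grade 3 or 4 row. This is a reason to expect a small gap, but it does not measure the gap.

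Finally, Appendix A plans participant-level listings of Grade 3 and 4, fatal and drug-related events, from which the overlap could be counted by hand. That is true, but a hand count from listings is not the tabulation that Protocol 10.4.2 describes.

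**Conclusion.** The mismatch between protocol and SAP is real and undeclared, and its reach is limited. It affects the overall-summary rows and, most firmly, treatment-related Grade 3 or higher TEAEs, which no planned table allows a reader to recover. All-cause incidence by SOC and PT is recoverable from Table 3.2.4, given the usual counting convention.

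The size of the understatement is unknown: between zero and the fatal-TEAE rate in each arm. The 3.7% should not be read as an estimate of it. It comes from one arm of a different disease setting and says nothing about a difference between arms. Because none of those three deaths was considered related to study treatment, it also does not size the treatment-related gap. A reader might infer that the tafasitamab arm will look safer than it is. That would require more participants with only a fatal severe event in that arm, and the documents give no evidence either way.

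No formal safety testing is planned, so no error rate, power or decision rule changes. This is a matter of delivering the stated safety analysis.

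**What to change.** In SAP 8.2.4 and Appendix A:

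- Add Grade 3 or higher rows to the overall summary (Table 3.2.1), all-cause and related to each of tafasitamab/placebo, lenalidomide and rituximab.
- Add Grade 3 or higher SOC/PT tables for all-cause and treatment-related TEAEs beside 3.2.5, 3.2.6, 3.2.15, 3.2.17 and 3.2.19.
- Keep the existing Grade 3 or 4 and fatal displays, which are informative in their own right.

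Subgroup versions are optional, since the protocol does not promise them. If the sponsor prefers the present layout, the minimum is to declare the departure in SAP 10.1, though that would not deliver the protocol's figure.

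The cost is SAP wording and a changed grade filter in existing programs. No new data are needed.

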2.1.4.6. Combination Therapy With Tafasitamab and Lenalidomide in Non-Hodgkin Lymphomas

In the single-arm, Phase 2 study in participants with R/R DLBCL (NCT02399085; L-MIND), among 80 participants evaluable for efficacy, the combination of tafasitamab plus lenalidomide achieved an ORR of 57.5% (46 of 80 participants), a CR rate of 40.0% (32 of 80 participants), and a median DoR of 34.6 months (95% CI: 26.1, NR). This combination treatment has received breakthrough therapy designation by the FDA and was recently approved (BLA 761163).

The safety data from this study indicate that tafasitamab in combination with lenalidomide is well tolerated in the population of patients with R/R DLBCL. The majority of events were CTCAE Grade 1 (840 of 1639 events) or Grade 2 (489 of 1639 events) and mild in intensity (1027 of 1639 events). The most frequently reported hematological TEAEs were neutropenia in 41 participants (50.6%), anemia in 30 participants (37%), thrombocytopenia in 25 participants (30.9%), leukopenia in 12 participants (14.8%), and febrile neutropenia in 10 participants (12.3%). Events of neutropenia were manageable with dose reduction/modification and treatment with G-CSF.

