The most frequently reported nonhematological TEAEs were coded under the SOC infections and infestations (59 participants [72.8%]). The majority were Grade 1 or Grade 2 and mild in intensity. The most frequently reported TEAEs within this SOC were under the category urinary tract infection (as defined per customized MedDRA query), experienced by 18.5% of participants. Thirty participants (37.0%) experienced an event under the category rash, 10 participants (12.3%) experienced an event under the category infective pneumonia, and 4 participants (4.9%) experienced an event under the category sepsis. In total, 9 participants (11.1%) experienced AESIs during the study including tumor flare and dermatitis allergic (3 participants [3.7%] each), basal cell carcinoma (second primary malignancy; 2 participants [2.5%]), and myelodysplastic syndrome (1 participant [1.2%]). The AESIs of basal cell carcinoma (1 event; Grade 2), myelodysplastic syndrome (Grade 4), and tumor flare (1 event; Grade 3) were serious; all other AESIs were nonserious. No participants experienced Grade ≥ 3 infusion-related reaction, tumor lysis syndrome, or cytokine release syndrome. No participants reported overdose during the study. Only 5 participants experienced an infusion-related reaction; all were Grade 1 in severity. In total, 42 participants (51.9%) experienced 78 serious TEAEs during the study. The most frequently reported serious TEAEs were coded under the SOC infections and infestations (21 participants [25.9%]). The most frequently reported Grade ≥ 3 serious TEAEs were pneumonia (7 participants [8.6%]) and febrile neutropenia (5 participants [6.2%]).

Eight participants (9.9%) died while on treatment, of which 3 (3.7%) were due to AEs (sudden death, cerebrovascular accident, respiratory failure); none of these deaths were considered related to study treatment. The remaining 5 deaths were due to disease progression.

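### Two infection-duration rows in SAP 8.2.4 (sepsis and urinary tract infection) are defined by terms that do not match their labels

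*SAP*

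**What the plan says.** SAP 8.2.4 (Adverse Event Summaries) announces a "Duration of TEAEs of the selected PTs and customized MedDRA queries" summary, which becomes Table 3.2.37.x in Appendix A for the FL, MZL, overall and Japanese overall populations. Two of its rows matter here.

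- The Grade 3 or higher sepsis row is defined by "SMQ 'sepsis' and SMQ 'agranulocytosis". No narrow or broad scope is given for either query, and nothing says how they combine.
- The urinary row begins "Urinary tract infection ≥ Grade 3 (HLT 'bladder infections and inflammations" and goes on to two more HLTs, the last being "Glomerulonephritis and nephrotic syndrome".

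The same list has its own row for low neutrophil counts, "Neutropenia ≥ Grade 3 (PTs 'neutropenia,' 'neutrophil count decreased", another for febrile neutropenia at all grades, and one for Grade 3 or higher events in the whole SOC infections and infestations. The infective pneumonia row states a narrow scope; the sepsis row does not. The section closes by requiring a reference listing of the selected events.

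**The concern.** By its name, agranulocytosis is a blood-cell disorder, and glomerulonephritis and nephrotic syndrome are diseases of the glomerulus. Neither name denotes an infection, yet each sits inside a row labelled as one. The SAP already treats low neutrophil counts as separate events in the same list, so the sepsis row, if pooled, may duplicate that row in part.

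Infections are among the main serious treatment-related risks named in Protocol 2.3. How long a septic episode lasts and how long a cytopenia lasts are different clinical quantities. A median duration taken over a mixture of the two describes neither, and a reader of the clinical study report would take the row label at face value.

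**Working it through.** The plan states no figure here, so the check is mainly a comparison of texts, followed by an illustration of possible size.

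**1. Urinary row.** SAP 8.2.4 defines it by three HLTs with no restriction to infections. Protocol 2.1.4.6, describing the earlier tafasitamab plus lenalidomide study, also uses a customised query for a urinary tract infection category, but reports that category within the SOC infections and infestations. The SAP records no such limit. As written, any Grade 3 or higher event under the glomerular HLT enters the row.

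**2. Sepsis row.** There are two ways to read "SMQ 'sepsis' and SMQ 'agranulocytosis".
- *Pooled (union).* This is the natural reading, because the other multi-term rows list terms to be pooled. Events found only by the agranulocytosis query then enter a row called sepsis.
- *Overlap only (intersection).* No event outside the sepsis query enters, but sepsis events outside the agranulocytosis query are lost.

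Under either reading the row is not simply sepsis, so the definition needs correcting.

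**3. Possible size of the pooled sepsis row.** Inputs from Protocol 2.1.4.6:
- "4 participants (4.9%) experienced an event under the category sepsis"; 4/81 = 4.9%.
- "neutropenia in 41 participants (50.6"%); 41/81 = 50.6%.

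Both percentages imply a denominator of 81. Assumption, not in the documents: a fraction f of participants with neutropenia is captured by the agranulocytosis query, with no overlap with the sepsis category, and that category contains only sepsis. Then

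non-sepsis share = 50.6f / (50.6f + 4.9).

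| f | Calculation | Non-sepsis share |
|---|---|---|
| 0 | 0 / 4.9 | 0% |
| 0.05 | 2.53 / 7.43 | 34% |
| 0.10 | 5.06 / 9.96 | 51% |
| 0.20 | 10.12 / 15.02 | 67% |
| 1 | 50.6 / 55.5 | 91% |

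At f = 1 the combined row would hold 45 of 81 participants (55.6%) with no overlap. If all four sepsis participants also had neutropenia it would hold 41 of 81 (50.6%), of whom 37/41 = 90% would have no sepsis event.

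These inputs are participant incidences with no grade limit stated, from a DLBCL study without rituximab. The SAP row concerns durations of Grade 3 or higher events in FL and MZL. The table shows only how sensitive the row is to the unknown f; it is not a forecast.

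**4. Urinary row size.** The documents give no rate for glomerular events, so no figure can be offered.

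**The case against.** The strongest objection is that a query's title is not its content. The member terms of the SMQs and HLTs are not in the documents, so the number of non-infectious events cannot be shown. That stands, and it is why only a range is given. It does not rescue the definitions: a component named for another disease, added without restriction or scope, leaves the programmer no instruction to keep the row to infections.

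The earlier study may also point the other way. It reported categories with the same names as the SAP rows, and its sepsis category stayed at 4 participants beside 41 with neutropenia. If that category used this same query, neutropenia does not swamp the row. The Protocol does not say how the category was defined, so this is unresolved. If a restriction kept it small, the SAP should record it.

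The intent may have been to catch neutropenic sepsis. That is plausible, and can be met by naming it.

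A reader might infer three stronger things that the documents do not support:

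- *That the sepsis row will be mostly neutropenia.* Any single share, such as 67%, depends on a capture rate the documents do not supply.
- *That a difference in sepsis between arms would be hidden.* Sepsis terms still appear by arm, undiluted, in the SOC and preferred-term tables for all, Grade 3 or 4, serious and fatal events (Tables 3.2.2.x, 3.2.5.x, 3.2.7.x and 3.2.24.x). The reference listing would also show which events were pooled.
- *That the infection-duration summaries as a whole are affected.* The SOC infections, infective pneumonia and opportunistic infection rows are not in question.

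**Conclusion.** The point holds as a minor defect of definition. Two rows of Table 3.2.37.x carry labels that their term lists do not match, and as written they can mix durations of non-infectious blood-cell and glomerular events into rows labelled as infections. For the sepsis row this rests on reading the two queries as pooled; on the overlap reading the row is wrong in a different way. The urinary point does not depend on that choice.

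The size is unknown: from nothing to most of the sepsis row, and unquantified for the urinary row. The safety analysis is descriptive, with no formal testing (SAP 8.1), and efficacy, type I error and sample size are not touched. What is at stake is the correct reading of two duration rows.

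**What to change.** Either of two edits to SAP 8.2.4 would do:

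1. Restrict both rows to terms in the SOC infections and infestations, in line with how Protocol 2.1.4.6 reports the urinary category; or
2. Remove the agranulocytosis SMQ from the sepsis row, naming neutropenic sepsis explicitly if it is wanted, and remove the glomerulonephritis and nephrotic syndrome HLT from the urinary row.

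In both cases, state the SMQ scope, as the pneumonia row already does, and state that multiple queries are pooled. The cost is a small change to two term lists before programming. The possible downside is a somewhat less sensitive search, since an event coded only under a removed term would drop out of these rows; it would still appear in the SOC and preferred-term tables.
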